### 4.3.6 Corneal Sequelae Associated with ECL

### 4.3.6.1 Statistical Hypotheses

No hypothesis testing of the endpoint is planned.

### 4.3.6.2 Analysis Methods

A listing of corneal sequelae associated with ECL will be provided.

### 4.3.7 Association between Peripheral and Central ECD Count and Number of Observed Rings

### 4.3.7.1 Statistical Hypotheses

No hypothesis testing of the endpoint is planned.

### 4.3.7.2 Analysis Methods

Summary statistics for peripheral ECD count will be provided, stratified by visit and by number of rings observed at the visit, for all COMPASS XXT study visits. Summary statistics for central ECD count will be provided, stratified by the number of rings observed at the visit, for all visits with available data from the COMPASS, COMPASS XT, and COMPASS XXT studies.

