5 INTRODUCTION

5.1 Rationale and Background

The COMPASS trial was a prospective, randomized, comparative multicenter study to assess the safety and effectiveness of the CyPass Micro-Stent in subjects with primary open angle glaucoma who were undergoing cataract surgery. In the study, a total of 505 subjects were randomized to one of two treatment groups, as follows: the CyPass group underwent cataract surgery and received the CyPass Micro-Stent, while the Control group underwent cataract surgery alone. All subjects randomized were followed for 24 months postoperatively, Vold 2016.

The study was performed in 2 phases. During the initial phase, 75 subjects were randomized. After FDA review of 3-month or longer postoperative data on these subjects, approval was granted for enrollment and randomization of the remaining 430 subjects in the study expanded phase. Enrollment in the initial study phase began in September 2009 and ended in August 2010. Enrollment in the expanded phase of the study began in July 2011 and the last study subject was randomized in March 2013.

The COMPASS XT trial was designed to collect safety data beyond 24 months postoperatively for subjects who completed the COMPASS trial until 60 months. Study enrollment was initiated April 2016 and the last subject visit occurred in April 2018, lanchulev 2019, and Reiss 2019.

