12.4.7.2 Analysis Methods

Summary statistics for peripheral ECD count will be provided, stratified by visit and by number of rings observed at the visit, for all COMPASS XXT study visits. Summary statistics for central ECD count will be provided, stratified by the number of rings observed at the

Document: TDOC-0056258 Version: 3.0; Most-Recent; Effective; CURRENT

Status: Effective Page 47 of 57

visit, for all visits with available data from the COMPASS, COMPASS XT, and COMPASS XXT studies.

12.4.8 Secondary Surgical Interventions (SSIs) to Modify the Device Position (eg, Repositioning, Trimming, Explanation)

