#### 9 Appendix A: Schedule of Study Procedures and Assessments

Table 9–1     Schedule of Study Procedures and Assessments				
Procedure	84-Month Visit (2555±120 days) Error! Reference source not found.	96-Month Visit (2920±120 days) Error! Reference source not found.	108-Month Visit (3285±120 days) Error! Reference source not found.	120-Month Visit/Exit Visit (3650±120* days) Error! Reference source not found.
Informed Consent Error! Reference source not found.	Х	Х	Х	Х
Demographics Error! Reference source not found.	Х	Х	Х	Х
Inclusion/Exclusion Error! Reference source not found.	Х	Х	Х	Х
Ocular Medical History	Х	Х	Х	Х
Ocular Surgical History	Х	Х	Х	Х
Monocular BCVA (ETDRS)	X	Х	Х	X
Pachymetry CCT	Х	Х	Х	X
Gonioscopy and Gonio photography 	Х	Х	Х	X
UBM/OCT 	Х	Х	Х	X
Slit-Lamp Exam	Х	Х	Х	X
Visual Field	Х	Х	X X	X
Fundus Exam with C:D Ratio	Х	Х	Х	X
Specular Microscopy (central and peripheral ECD)	Х	Х	Х	X
Ocular AE Assessment 	Х	Х	Х	Х
Device Deficiencies	X	Х	Х	X

Table 9–1Schedule of Study Procedures and Assessments

1. Annual visits are required until 10 years post-CyPass implantation is reached. Not all visits are required for every subject. The number of study visits required to be completed will coincide with the number of months following CyPass implantation. Note: All subjects from COMPASS have surpassed the 72-month follow-up period.

\*For subjects who have reached the 10 years post-CyPass implantation at the time of study initiation, the +120day visit window does not apply. Alcon - Business Use Only Statistical Analysis Plan Effective Date: 2020-04-29 08:59:45
Document: TDOC-0057258 Version: 3.0; Most-Recent; Effective; CURRENT
Status: Effective

- 2. Informed consent, demographics, and inclusion/exclusion criteria assessments are only required at the first study visit.
- 3. Gonio photography to be assessed objectively for evaluating device position.
- 4. Optional if available at the site.
- 5. Any ocular AEs occurring since the Exit visit from COMPASS or COMPASS XT (whichever was last study visit) will be captured. These include but are not limited to corneal haze/edema, device malposition, device explantation, device trimming, and/or device repositioning.

6.

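### Central ECD by ring count is not split by visit, unlike peripheral ECD, so as written the table pools visits up to 10 years apart and counts eyes repeatedly and unequally.

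*SAP*

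**What the plan says.** SAP 4.3.7.2 gives two rules in adjacent sentences.

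- Peripheral ECD: "Summary statistics for peripheral ECD count will be provided, stratified by visit and by number of rings observed at the visit", restricted to COMPASS XXT visits.
- Central ECD: "Summary statistics for central ECD count will be provided, stratified by the number of rings observed at the visit", and this is to be done "for all visits with available data from the COMPASS, COMPASS XT, and COMPASS XXT studies".

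Protocol 12.4.7.2 has the same pair of rules; its central sentence again begins "Summary statistics for central ECD count will be provided, stratified by the number of rings observed at the" visit, with no visit stratum. An SAP typing slip is therefore an unlikely explanation.

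The other central ECD summaries are by visit (SAP 4.3.3.2 and 4.3.4.2) or by year of observation (SAP 4.3.5.2). For the ring endpoint, neither document states an adjustment for time since implantation, a within-eye method or a one-record-per-eye rule. No hypothesis test is planned (SAP 4.3.7.1), and SAP 4.3.7.2 specifies no confidence interval.

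**The concern.** The summary without a visit stratum is the one with the longer time span. Peripheral ECD covers only the XXT visits, scheduled at 84 to 120 months. Central ECD also takes in COMPASS, where "All subjects randomized were followed for 24 months postoperatively", and COMPASS XT, which collected data "for subjects who completed the COMPASS trial until 60 months".

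Two problems follow if the rows are pooled.

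1. **Time.** ECD may fall over follow-up; SAP 4.3.5 exists to ask whether the loss stabilises. Ring count can change within an eye: Protocol 11.1.1(dd) defines device movement by such a change. If the ring distribution shifts with time, the pooled ring strata differ in follow-up time, and a time trend in ECD appears as a ring difference.
2. **Eyes.** An eye enters once per visit with data, and the number of visits differs between eyes. The count in a stratum is then eye-visits, weighted towards eyes seen more often.

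This is the only planned analysis that crosses central ECD with ring count. SAP 4.3.16.4 and 4.7 tabulate ring counts but do not cross them with ECD, so no other planned table would expose a time artefact.

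**Working it through.** The plan states no figure for this endpoint, so there is none to reproduce. The 374 in SAP 7 is the number implanted, not a power calculation.

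**Step 1: the two rules side by side**

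| | Peripheral ECD | Central ECD |
|---|---|---|
| Strata named | visit and ring count | ring count only |
| Studies | XXT | COMPASS, XT and XXT |
| Scheduled span | 84 to 120 months | COMPASS follow-up to 120 months |

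**Step 2: how unequally eyes contribute**

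SAP Appendix A schedules up to four XXT visits, but "Not all visits are required for every subject". Protocol 5.1 gives COMPASS enrolment as September 2009 to August 2010 and July 2011 to March 2013. The earliest target date in Protocol Table 7-1 is May 2020. Taking implantation as close to enrolment:

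- August 2010 + 108 months = August 2019; adding 120 days gives December 2019, before May 2020. Initial-phase eyes can therefore have only the 120-month visit.
- January 2013 + 84 months = January 2020; adding 120 days gives about May 2020. Only eyes implanted from about January 2013 could still have an 84-month visit.

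An eye thus supplies one to four XXT records. It may or may not have XT records, since 215 of the 374 entered XT (SAP 7).

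**Step 3: size of the time effect, under assumptions**

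The documents do not give the ECD level, spread, slope, within-eye correlation or ring distribution. Assumed:

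- 215 eyes (the XT enrolment), with complete data at months 6, 24, 60, 84, 96, 108 and 120
- mean ECD 2300 and SD 400 cells/mm², within-eye correlation 0.7
- linear slope s of −20, −50 or −80 cells/mm² per year
- 20% of eyes in the higher ring group at month 6, with that share moving linearly by 0, +10, +20 or −10 percentage points by month 120
- no ring effect on ECD at any visit

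With p(t) the share in the higher ring group at t years, the expected pooled difference (higher minus lower) is

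s × [Σp·t/Σp − Σ(1−p)·t/Σ(1−p)],

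that is, slope times the difference in mean follow-up time. The seven visit times sum to 41.5 years.

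- No shift: both means are 41.5/7 = 5.93 years. The difference is 0.
- +10 points: Σp = 1.8 and Σp·t = 11.484, so 11.484/1.8 − 30.016/5.2 = 6.380 − 5.772 = 0.608 years.
- +20 points: Σp = 2.2 and Σp·t = 14.668, so 14.668/2.2 − 26.832/4.8 = 6.667 − 5.590 = 1.078 years.
- −10 points: Σp = 1.0 and Σp·t = 5.116, so 5.116/1.0 − 36.384/6.0 = 5.116 − 6.064 = −0.948 years.

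Expected pooled difference in cells/mm², with the mean of 400 simulated replicates in brackets:

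| Shift | s = −20 | s = −50 | s = −80 |
|---|---|---|---|
| 0 | 0 (−6) | 0 (−9) | 0 (−1) |
| +10 points | −12 (−14) | −30 (−30) | −49 (−45) |
| +20 points | −22 (−20) | −54 (−52) | −86 (−84) |
| −10 points | +19 (+22) | +47 (+52) | +76 (+75) |

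In the same simulations, comparing ring groups within visit and averaging over visits gave −9 to +4, against a true value of 0. The formula gives exactly 0 with no shift, so those departures are simulation error.

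These runs use complete data. They do not include the changing mix of eyes in Step 2, which is a second route to the same distortion.

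**Step 4: repeated eyes**

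215 eyes × 7 visits = 1505 records. For an overall mean the design effect is 1 + (7 − 1) × ICC, where ICC is the within-eye correlation:

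- ICC 0.5: 1505/4.0 = about 376 independent records
- ICC 0.7: 1505/5.2 = about 289
- ICC 0.9: 1505/6.4 = about 235

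At ICC 0.7 the simulated standard error of the pooled ring difference was about 1.8 to 2.5 times the one that treats records as independent. This holds with or without a ring shift.

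**The case against.** **Pooling is an inference.** The central sentence refers to rings seen at the visit and then lists the visits covered. The peripheral sentence ends the same way with "stratified by visit and by number of rings observed at the visit, for all COMPASS XXT study visits", where the closing phrase only sets scope. Since the other central ECD summaries are by visit or year, one table per visit is a possible reading. It is the weaker one, because visit is named as a stratum in the sentence before and absent here. If it is what the sponsor means, the same edit settles it.

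**The bias needs a shift that the documents do not report.** This stands. A reader might infer that the pooled table will be biased, perhaps heavily. A steady gain of 0.1 or 0.2 ring per year would produce sizeable differences between extreme ring strata. From 0.5 to 10 years, however, that is 0.1 × 9.5 = 0.95 or 0.2 × 9.5 = 1.9 rings for the average eye. Protocol 11.1.1(dd) treats a change of at least 1 ring, not explained by viewing or anatomy, as a device movement event. Nothing in the documents supports a cohort-average shift of that order.

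**The inflation of n.** A reader might also multiply the number of eyes by the full visit schedule. Step 2 of the working shows that few eyes could reach such a ceiling.

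**No inferential harm.** The endpoint is descriptive, with no test and no interval for it, so no error rate, interval width or sample size is affected. This also stands. What remains is a descriptive table that could mislead about the association it is named for. The by-visit ECD and ring tables would show time trends separately, but they do not cross the two.

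**Sparse cells.** Central ECD spans three studies, so visit-by-ring cells may be thin. That is a real cost and is weighed in the fix.

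**Conclusion.** The point holds in a limited form. Both documents name visit as a stratum for peripheral ECD and omit it for central ECD, and pooling is the natural reading of the central sentence. Followed as written, the only planned summary of central ECD against ring count mixes follow-up times and counts eyes repeatedly and unequally.

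Whether that misleads depends on facts that the documents do not supply. If ring counts or the contributing eyes shift over follow-up while ECD falls, the table can create or hide an association. Under the assumptions in the working, the simulated artefact was −14 to −84 cells/mm² for an upward ring shift and +22 to +75 for a downward one. With no shift the time bias is about zero, and only the repeated, unequally weighted eyes remain. These figures illustrate the mechanism; they are neither estimates for this cohort nor bounds.

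The change should be made because it is cheap and this table has no back-up, not because a bias has been shown.

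**What to change.** In SAP 4.3.7.2 and Protocol 12.4.7.2, add visit as a stratum for central ECD, in the form already used for peripheral ECD. For example: *Central ECD will be tabulated by visit and, within visit, by number of visible rings, for every COMPASS, XT and XXT visit with both measurements. Each cell will give the number of eyes.* If a row pooled over visits is kept, report both eyes and eye-visits for it and label it as unadjusted for time.

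No new data are needed. The cost is a longer table with some small cells; adjacent ring counts may need to be grouped, with the grouping fixed before the data are seen.

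A repeated-measures model of central ECD on ring count, with time since implantation as a covariate and eye as a random effect, is optional. It is worth adding only if a single overall figure is wanted, since it goes beyond the plan's descriptive intent.

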### 4.3.8 Secondary Surgical Interventions (SSIs) to Modify the Device Position (eg, Repositioning, Trimming, Explanation)

### 4.3.8.1 Statistical Hypotheses

No hypothesis testing of the endpoint is planned.

### 4.3.8.2 Analysis Methods

A listing of SSIs to modify the device position will be provided.

### 4.3.9 Effects of SSIs on Central and Peripheral ECD

### 4.3.9.1 Statistical Hypotheses

No hypothesis testing of the endpoint is planned.

### 4.3.9.2 Analysis Methods

A listing of central and peripheral ECD measurements will be produced for subjects with SSIs. The date of the SSI will be noted in this listing for each subject.

### 4.3.10 CyPass Micro-Stent Movement and/or Malposition

### 4.3.10.1 Statistical Hypotheses

No hypothesis testing of the endpoint is planned.

### 4.3.10.2 Analysis Methods

The rate of all CyPass Micro-Stent movement and/or malposition will be presented with a count and percentage, and will be accompanied by a two-sided exact binomial 95% confidence interval.

### 4.3.11 Corneal AEs (eg, Corneal Decompensation, Tube Corneal Touch, Corneal Edema, etc.) Caused by CyPass® Micro-Stent

### 4.3.11.1 Statistical Hypotheses

No hypothesis testing of the endpoint is planned.

### 4.3.11.2 Analysis Methods

A listing of corneal AEs caused by the CyPass Micro-Stent will be provided, which will include central and peripheral ECD measurements, where available.

### 4.3.12 Losses in Best Corrected Visual Acuity (BCVA) ≥ 10 letters

### 4.3.12.1 Statistical Hypotheses

No hypothesis testing of the endpoint is planned.

### 4.3.12.2 Analysis Methods

A listing of BCVA loss of 10 letters or more will be provided, and will include all available BCVA data from the COMPASS, COMPASS XT, and COMPASS XXT studies for the subject. BCVA loss of 2 lines (10 letters) or more will be reported as an adverse event, so adverse event data will be the data source for this analysis.

### 4.3.13 Change in Visual Field Mean Deviation (MD)

### 4.3.13.1 Statistical Hypotheses

No hypothesis testing of the endpoint is planned.

### 4.3.13.2 Analysis Methods

Change in visual field mean deviation at each visit postoperative as compared to the recorded value at the COMPASS screening visit will be reported. Observed values and change from screening values will be presented descriptively (N, mean, median, standard deviation, standard error, minimum, and maximum) at each study visit for each device.

Counts and percentages of subjects will be presented according to the following categories: increase > 2.0 dB; no change (-2.0 to 2.0 dB); decrease > 2.0 dB. Denominators will consist of the number of subjects with non-missing visual field data at both time points.

### 4.3.14 Change in Central Corneal Thickness

### 4.3.14.1 Statistical Hypotheses

No hypothesis testing of the endpoint is planned.

### 4.3.14.2 Analysis Methods

Change in central corneal thickness from baseline at each follow-up visits will be summarized. A mean, standard deviation, minimum, median, maximum, and a 95% confidence interval based on the t-distribution will be provided for the change and percentage change from baseline at each visit.

### 4.3.15 Adverse Events

All adverse events reported to Alcon will be accounted for in the reporting. Since some of the data collection for this study will be retrospective, some of the adverse events will have occurred prior to the date of informed consent. Descriptive summaries (counts and percentages) and listings will be presented.

The applicable definition of an Adverse Event (AE) is in the study protocol.

### 4.3.16 Other Safety Outcomes

### 4.3.16.1 Best Corrected Visual Acuity (BCVA)

BCDVA (collected in letters read) will be summarized at each post-operative visit at which BCDVA is collected; change from baseline (COMPASS Baseline visit) will also be summarized at each postoperative visit at which BCDVA is collected. Data will be summarized based on the visual acuity score (letters read).

Best corrected visual acuity will also be converted to Snellen values and summarized categorically by the following groupings for each scheduled visit: 20/20 or better; 20/25 or better; 20/32 or better; 20/40 or better; worse than 20/40; missing; discontinued. Details for this conversion can be found in Appendix B.

### 4.3.16.3 Corneal Pachymetry

Central corneal thickness will be summarized at each follow-up visit with n, mean, standard deviation, minimum, median, and maximum. A 95% confidence interval based on the t-distribution will be provided for the change and percentage change from baseline. This will be measured three times for each subject for each visit, and the median value will be used to calculate summary statistics.

### 4.3.16.4 Gonioscopy

Gonioscopy at baseline (COMPASS Baseline visit) and at each COMPASS XXT follow-up visit at which the exams are conducted will be summarized with counts and percentages of number of rings visible. A listing will accompany this summary.

### 4.3.16.5 Slit Lamp Findings

Slit lamp results at baseline (COMPASS Baseline visit) and at each COMPASS XXT followup visit at which the exams are conducted will be summarized by the number of abnormal findings in each category (numerator), the number of observations with data (denominator). A listing will be provided which presents all subjects with any abnormal slit lamp findings.

### 4.3.16.6 Visual Field Loss Mean Deviation Testing

The visual field mean deviation (dB) testing data will be summarized for each visit. A categorical summary of changes from screening will be presented using the following three categories: Increase ( $\geq 2.5$  dB), No Change (-2.5 < dB to < 2.5 dB), or Decrease ( $\leq -2.5$  dB).

### 4.3.16.7 Dilated Fundus Examination

The fundus examination includes ophthalmoscopic assessments of the vitreous, retina, macula, choroid, and optic nerve of both eyes. A frequency table of dilated fundus findings by visit will be presented.

### 4.3.16.8 Device Deficiencies

The applicable definition of a device deficiency is in the study protocol. A frequency table showing counts for each Device Deficiency category will be presented. In addition, a listing all device deficiencies, as recorded on the Device Deficiency Form will be provided.

### 4.4 Interim Analysis for Safety

Interim reports pertaining to the progress of the post-approval study will be submitted to the FDA for review every 6 months for the first 2 years and annually thereafter, starting from the date of FDA approval of the protocol, until study completion.

### 4.5 Multiplicity Strategy

No statistical testing will be performed so no multiplicity adjustments are necessary.

### 4.7 Comparison of COMPASS XXT Subjects to Original COMPASS Subjects Implanted with CyPass

Analysis will be conducted to compare subjects followed in this COMPASS XXT study to the full CyPass cohort implanted in the COMPASS trial.

ECD at baseline will be summarized for the two cohorts (COMPASS XXT vs. COMPASS). These summaries will include number of eyes, mean, standard deviation, and the following percentiles: 0th, 5th, 25th, 75th, 95th, and 100th.

The number and percent of eyes having ECD<1000 will be reported for each cohort at 6 months and 24 months.

The within-eye ECD loss from baseline and % ECD loss from baseline at 6 months and 24 months will be summarized for the two cohorts These summaries will include the number of eyes, mean, standard deviation, and the following percentiles: 0th, 5th, 25th, 75th, 95th, and 100th.

The within-eye ECD loss from 6 months to 24 months, and the % ECD loss from 6 months to 24 months will be summarized for the two cohorts. These summaries will include the number of eyes, mean, standard deviation, and the following percentiles: 0th, 5th, 25th, 75th, 95th, and 100th.

The number and percentage (specifying the denominator) of eyes with each level of observed rings at the 24 months visit will be reported for each cohort.

Printed By:

### 6 Handling of Missing Data

Missing data imputation will not be performed.

### 7 Sample Size and Power Calculations

Sample size (374) is based on the number of subjects who were implanted with a CyPass Micro-Stent in the COMPASS trial. It is not based on statistical power. 374 subjects were implanted with CyPass in the COMPASS trial. Of these, 215 volunteered to enroll in COMPASS XT. The total enrolled in this trial will be a subset of the 374 COMPASS CyPass subjects, is not restricted to those enrolled in COMPASS XT, and may be above or below the total enrolled in the COMPASS XT trial.

#### 9 Appendix A: Schedule of Study Procedures and Assessments

Table 9–1     Schedule of Study Procedures and Assessments				
Procedure	84-Month Visit (2555±120 days) Error! Reference source not found.	96-Month Visit (2920±120 days) Error! Reference source not found.	108-Month Visit (3285±120 days) Error! Reference source not found.	120-Month Visit/Exit Visit (3650±120* days) Error! Reference source not found.
Informed Consent Error! Reference source not found.	Х	Х	Х	Х
Demographics Error! Reference source not found.	Х	Х	Х	Х
Inclusion/Exclusion Error! Reference source not found.	Х	Х	Х	Х
Ocular Medical History	Х	Х	Х	Х
Ocular Surgical History	Х	Х	Х	Х
Monocular BCVA (ETDRS)	X	Х	Х	X
Pachymetry CCT	Х	Х	Х	X
Gonioscopy and Gonio photography 	Х	Х	Х	X
UBM/OCT 	Х	Х	Х	X
Slit-Lamp Exam	Х	Х	Х	X
Visual Field	Х	Х	X X	X
Fundus Exam with C:D Ratio	Х	Х	Х	X
Specular Microscopy (central and peripheral ECD)	Х	Х	Х	X
Ocular AE Assessment 	Х	Х	Х	Х
Device Deficiencies	X	Х	Х	X

Table 9–1Schedule of Study Procedures and Assessments

1. Annual visits are required until 10 years post-CyPass implantation is reached. Not all visits are required for every subject. The number of study visits required to be completed will coincide with the number of months following CyPass implantation. Note: All subjects from COMPASS have surpassed the 72-month follow-up period.

\*For subjects who have reached the 10 years post-CyPass implantation at the time of study initiation, the +120day visit window does not apply. Alcon - Business Use Only Statistical Analysis Plan Effective Date: 2020-04-29 08:59:45
Document: TDOC-0057258 Version: 3.0; Most-Recent; Effective; CURRENT
Status: Effective

- 2. Informed consent, demographics, and inclusion/exclusion criteria assessments are only required at the first study visit.
- 3. Gonio photography to be assessed objectively for evaluating device position.
- 4. Optional if available at the site.
- 5. Any ocular AEs occurring since the Exit visit from COMPASS or COMPASS XT (whichever was last study visit) will be captured. These include but are not limited to corneal haze/edema, device malposition, device explantation, device trimming, and/or device repositioning.

6.

